Effects of Walking Out From Operating Room on Postoperative Recovery
of Patients Undergoing Laparoscopic Total or Partial Nephrectomy.

Study protocol

Document Date: May 19, 2019

After receiving the approval from institutional ethical committees, we will obtain written informed consent from 182 patients undergoing laparoscopic total or partial nephrectomy with American Society of Anesthesiology physical status I and II and aged 18 to 65 years. A sample size of 91 patients in each group was selected by a prior power analysis on the basis of the following assumptions: (1) an absolute reduction in the length of the hospital stay by 1 day, (2) standard deviation 2 days, (3) $\alpha=0.05$, (4) power 90% and (5) missed follow-up rate 5%

Patients will be excluded if they have severe cardiac diseases (cardiac function grading greater than grade 3/arrhythmia including sick sinus syndrome, atrial fibrillation, atrial flutter, atrioventricular block, frequent ventricular premature, multiple ventricular premature, ventricular premature R on T, ventricular fibrillation and ventricular flutter/acute coronary syndrome), or respiratory failure, or hepatic failure, or renal failure, or diabetics, or body mass index (BMI) $\geq 30 \text{ kg/m}^2$, or patients gastric emptying disorders, or poor blood pressure control (receive regular antihypertensive medical treatment but still have systolic blood pressure $> 150 \text{ mmHg}$ and/or diastolic blood pressure $> 90 \text{ mmHg}$), or have schizophrenia, epilepsy, Parkinson's disease, mental retardation, or hearing impairment, or have thrombosis such as in lower extremity or in vena cava or in renal vein or in other veins, or have neuromuscular disorders affecting lower limb activity, such as myasthenia gravis and cerebral infarction, which cause lower limb muscle weakness, or have contraindications for epidural puncture, or participate in other clinical trials, or refuse to sign informed consent for research.

The randomization will take place before the day of the surgery and the patients will be assigned to either intervention (return to ward by walking) or control group (return to ward by lying on the transporting bed). A stratified randomization with three factors including sex, disease character and age will be performed by statistician to ensure an even spread. The randomization is performed externally using a randomization list prepared by a statistician. This process will be blinded and remote to the investigator. The allocation was communicated by the trial coordinator using

concealed envelopes.

The standardized process of perioperative management are as follow:

1. Preoperatively, all patients do not receive bowel preparation.

2. All patients take oral hydration oral hydration diet 11 hours before entering the operating room and take another oral hydration 2 hours before entering the operating room.

3. Operation bed is warmed by warm blanket before the patient lying down and is kept warm during the operation.

4. An epidural (T9–10) catheter is inserted with a test dose of 1% lidocaine (3ml) . If symptoms of total spinal anesthesia do not appear 5 minutes later, morphine (2mg diluted in 5 ml normal saline) is injected through the epidural catheter .

5. Bispectral Indexes (BIS) is monitored before induction of general anesthesia. General anesthesia is induced by propofol (2-2.5 mg/kg), fentanyl (4 μ g/kg), and cisatracurium 0.15 mg/kg. The propofol and fentanyl are infused by pump individually. Before the anesthesia induction, dexamethasone (5 mg) is given intravenously to prevent nausea and vomiting after operation, Flurbiprofen Axetil (50mg) is given to decrease postoperative pain and Lansoprazole (30mg) is given to attenuate the gastrointestinal side effects .

6. The ventilation parameters are as follows: fresh gas flow rate 2 L/min, inhaled oxygen concentration 50%, tidal volume 7 ml/kg (ideal body weight) , PEEP 6-8 cmH₂O, respiratory frequency 12 times/min(timely adjusted according to the end-expiratory CO₂ partial pressure).

7. General anesthesia is maintained by sevoflurane (about 0.8MAC) in combination with remifentanil (0.02-0.08 μ g/kg/min) and dexmedetomidine (0.2-0.3 μ g/kg/h) to keep BIS 50±10.

8. Thirty minutes before the end of the operation: (1) 0.2% ropivacaine (7ml) is given through epidural catheter, and then the epidural analgesia pump was connected (formula: 0.2% ropivacaine, background flow 1.5 ml/h, bolus 1.5 ml, lock time 20 minutes); (2) Flurbiprofen Axetil (50mg) is given intravenously;(3) intravenous

palonosetron 0.25 mg to prevent nausea and vomiting;(4) The infusion of dexmedetomidine is stopped;(5) The inhalation of sevoflurane is stopped and the flow of fresh gas is reduced to 0.3-0.5 L/min;(6) The flow of fresh gas is increased to 5 L/min until the skin is sutured in order to speed up the washing of sevoflurane; (7) 0.2% ropivacaine (10ml) is irrigated in the renal fossa prior to surgical closure; (8) After the suture skin is completed, 0.5% ropivacaine (10ml) is used for incision infiltration anesthesia.

9. After surgery, the patient is transferred to post-anesthesia recovery room and evaluated whether fulfilling the criteria for mobilization including stable physiological parameters, clear consciousness, normal level of orientation and muscle strength, and painlessness every ten minutes. If patients fulfill the criteria, they will receive different methods of returning to the ward based on the grouping. In the control group, the patient will return to the ward by lying on the transporting bed. In the intervention group, the patients will be raised to a sitting position for five minutes. If the patients do not complain any discomfort and have stable physiological parameters, they will be encouraged to stand. If standing do not cause any discomfort, they will be encouraged to walk within the range of 5-meter long and 60-centimeter wide. If patients can walk within the range, they will return to the surgical ward by walking. However, if patients in the intervention group cannot sitting, they will return to the surgical ward by lying on the transporting bed. If patients can sit but cannot stand or walk, they will return to the surgical ward by sitting in the wheel chair.

Then, all study patients will be subject to the same management such as the guidance of drink and diet recovery, the guidance of mobilization in the ward (the duration and distance of walking in the ward will be recorded every day), nutrition supplement after surgery, and the criteria of drainage removal and hospital discharge. The outcomes such as the length of hospital stay after surgery will be recorded and analyzed to evaluate the effects of walking out from the operating room.

Recovery time, which is considered an ideal time point for discharge. The criteria for measuring recovery time included: 1) tolerance of diet and not necessary for

intravenous nutrition; 2) analgesic-free, which is defined as visual analogue scale ≤ 3 without intravenous analgesic drugs, 3) adequate mobility; 4) afebrile status without major infectious complications (fever is defined as body temperature greater than 37.2°C at axilla). Patients are discharged when they consider themselves sufficiently recovered after the recovery time.

Statistical analysis Mean (SD) for normally distributed data or median (Q1, Q3) for skewed data will be calculated for continuous variables, and frequency (percentage) will be generated for nominal or ordinal variables. As to inferential analysis, continuous variables will be analyzed with Student's t test or Mann-Whitney U test or Analysis of Variance for Repeated Measures. Mann-Whitney U test will also be used to the ordinal variables. Categorical outcomes will be analyzed with χ^2 test or Fisher's exact test. The analysis of Intention-to-treat and Per-protocol sets will be both performed by statisticians.

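### Does daily ward walking need its own analysis rule because discharged patients drop out of the series?

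*Combined protocol and SAP*

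**What the plan says.** The paragraph on ward care after item 9 of the perioperative process lists management that is the same in both arms. Within it, in a parenthesis on mobilization guidance, stands the only reference to ward walking data: "the duration and distance of walking in the ward will be recorded every day". The next sentence names one outcome as an example: "The outcomes such as the length of hospital stay after surgery will be recorded and analyzed".

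The Statistical analysis paragraph offers three methods for continuous variables: the t test, then "Mann-Whitney U test or Analysis of Variance for Repeated Measures". None is tied to a variable, and nothing is said about analysis days or days after discharge.

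Two other places bear on when a walking record ends. Recovery time has four criteria, one of which is "adequate mobility". After that the patient decides: "Patients are discharged when they consider themselves sufficiently recovered after the recovery time". The sample-size statement plans for "an absolute reduction in the length of the hospital stay by 1 day" with "standard deviation 2 days".

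**The concern.** A walking series that ends at discharge has a length tied to recovery, and mobility is part of recovery. Repeated-measures ANOVA is the only listed method meant for repeated data, and in its usual form it keeps only patients with every analysed day present. If it were run past the first discharges, everyone who left before the last day would be dropped. A t test or Mann-Whitney test on that last day alone would keep the same reduced set.

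The trial is designed to shorten stay in one arm, so the losses would be unequal. If the patients who remain are the poorer walkers, the intervention arm would be the more heavily selected, and its walking would look worse than it is. A real benefit could be understated and power lost.

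**Working it through.** **The plan's own figure.** Difference 1 day, SD 2, alpha 0.05 (taken as two-sided), power 90%, loss 5%. The normal approximation gives 2 x (1.960 + 1.282)^2 x 2^2 / 1^2 = 84.06, so 85 per group, and 85/0.95 = 89.5, so 90. The t-based solution is 85.03, so 86, and 86/0.95 = 90.5, so 91. The stated 91 per group reproduces. It concerns length of stay and does not depend on walking.

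**Inputs for the walking check.** From the documents: 1-day gap, SD 2, 91 per arm. Assumed, because the documents give none of them: control mean stay m of 5 to 8 days, a day 1-5 analysis, walking SD 50 m, true benefit 25 m, within-patient correlation 0.6, and fitness-stay correlation r of -0.5 or -0.2.

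**Retention.** A patient has a full day 1-5 series if stay is at least 5 days. With normal stay, the share kept is 1 - Phi(z), where z = (5 - m)/2 for control and (5 - (m - 1))/2 for intervention.

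**Bias.** The stable part of walking has SD 50 x sqrt(0.6) = 38.7 m. Among those kept, its mean shifts by r x 38.7 x L(z), where L(z) = phi(z)/(1 - Phi(z)). The bias is r x 38.7 x [L(z intervention) - L(z control)].

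**Standard error.** sqrt(2500 x (0.6 + 0.4/5) x (1/n_c + 1/n_i)), with n = 91 x share kept.

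At m = 6, r = -0.5: z is -0.5 and 0, L is 0.509 and 0.798, and the bias is -0.5 x 38.7 x 0.289 = -5.6 m. With n of 62.9 and 45.5, the standard error is sqrt(1700 x 0.0379) = 8.0 m, and 5.6/8.0 = 0.70.

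| Control mean (days) | Kept, control v intervention | Estimate of 25 m, r = -0.5 | Standard error | Bias / SE |
|---|---|---|---|---|
| 5 | 50% v 31% | 18.3 m | 9.9 m | 0.67 |
| 6 | 69% v 50% | 19.4 m | 8.0 m | 0.70 |
| 7 | 84% v 69% | 20.7 m | 7.0 m | 0.61 |
| 8 | 93% v 84% | 22.1 m | 6.5 m | 0.44 |

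Simulation gives the same estimates within its error of 0.1 to 0.2 m. With gamma-shaped stay the simulated estimates are 18.3, 18.5, 19.8 and 21.6 m with standard errors 10.6, 8.4, 7.1 and 6.5 m; the ratios are 0.63, 0.77, 0.73 and 0.52. At r = -0.2 the bias is at most 2.7 m.

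**How firm the ratio is.** The walking SD cancels from bias/SE, and the size of the benefit does not enter it. The within-patient correlation moves it modestly: at m = 5, normal, r = -0.5, a value of 0.3 gives 4.7/8.0 = 0.59 and 0.9 gives 8.1/11.5 = 0.71. The fitness-stay correlation matters most. By these formulas, bias would equal one standard error at about r = -0.72 (normal) or -0.65 (gamma), both at m = 6.

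**When nothing happens.** With no difference in stay (m = 5, r = -0.5), simulation returns 25.3 m (normal) and 25.0 m (gamma). If only day 1 is compared, at least 93% of each arm is still present in the worst normal case (98% v 93% at m = 5).

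**The case for a change.** The best case for a change is that it is cheap and the outcome list is open-ended, so walking may well be tested. The trial builds in unequal discharge, so late-day comparisons are distorted by design if the treatment works. Power suffers even without any link between fitness and stay: with gamma stay and zero correlation, a complete day 1-5 analysis has 63% power at a control mean of 5 and 85% at 6, against 91 to 98% in an early window. All of that stands as conditional arithmetic.

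It does not show that a planned analysis is wrong. The plan nowhere says walking will be compared; the log reads equally well as monitoring of standardised care. The repeated-measures option may be meant for other data, such as pain scores or the recovery-room checks, whose list of criteria ends "painlessness every ten minutes". Bias needs a walking comparison, late days, an analysis limited to those still present, a shorter stay, and fitter patients leaving sooner. The documents support only the shorter stay, and that as a planning assumption. Mobility is one of four recovery criteria, and the patient's own judgement then decides.

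The obvious remedy is a fixed early window in which at least 95% of both arms remain, with a mixed model inside it. It is not a clear gain:

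- It gives up formal testing of later days.
- The window shrinks to day 1 at a control mean of 5 under gamma stay, and at 5 and 6 under normal stay. With one record per patient, the mixed model is then only an adjusted two-group comparison. At 5 under normal stay, even day 1 misses 95%.
- If the target is walking while in hospital, the mixed model estimates something else: day means as though discharged patients had stayed.
- Under gamma stay at -0.5, the mixed model over all of days 1-5 with no window gives 24.4 and 24.8 m at means of 7 and 8. Complete-series analysis inside the window gives at most 24.3 m. At those means the window adds little that a model keeping partial series does not.

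**Conclusion.** No change is called for. The plan is silent on how, or whether, ward walking is compared; that is missing detail on a process measure, not an error. Analysts who did compare it would see the numbers fall at each discharge and could choose early days, or a method that keeps partial series, without any amendment.

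If they did neither and every condition held, the shortfall on an assumed 25 m benefit would be about 3 to 7 m at a correlation of -0.5, or 0.4 to 0.8 of a standard error, and at most 2.7 m at -0.2. Power would also fall where the control mean stay is short. These sizes rest on an assumed mean stay, window, walking SD, within-patient correlation and fitness-stay correlation, so the documents cannot fix them. A fitness-stay correlation stronger than about -0.65 would be needed for the bias to reach one standard error. Length of stay, the one outcome the protocol names and the basis for 91 per group, is unaffected in every case.

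### Does the recovery-time pain criterion need changing because it can be met while the epidural pump is still running?

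*Combined protocol and SAP*

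**What the plan says.** The protocol paragraph on recovery time, just before the statistical analysis paragraph, introduces the measure as "Recovery time, which is considered an ideal time point for discharge". Four criteria follow: diet, pain, mobility, and absence of fever or major infection. The pain criterion reads "analgesic-free, which is defined as visual analogue scale ≤ 3 without intravenous analgesic drugs". The paragraph closes with the discharge rule: "Patients are discharged when they consider themselves sufficiently recovered after the recovery time".

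The epidural appears earlier. Step 8 of perioperative management, timed thirty minutes before the end of the operation, gives a ropivacaine dose through the catheter "and then the epidural analgesia pump was connected", with the settings "0.2% ropivacaine, background flow 1.5 ml/h, bolus 1.5 ml, lock time 20 minutes". The numbered steps are introduced by "The standardized process of perioperative management are as follow", and step 8 makes no distinction between arms. Patients are excluded if they "or have contraindications for epidural puncture", so the pump is planned for everyone. The document gives no planned duration for the pump, no removal rule, and no condition that it be off before recovery is declared.

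**The concern.** The criterion rules out intravenous analgesics, yet the last intravenous analgesic that the protocol schedules is flurbiprofen, thirty minutes before the end of surgery. The one analgesic set up to continue afterwards is the epidural infusion, which the criterion does not mention. The pain score does not close the gap, because the pump may itself be what keeps the score at or below 3. Nor does the mobility criterion: in step 9, intervention patients sit, stand and walk after the pump was connected, and no disconnection is described.

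Two things would be at stake. First, a reader might take recovery time to mark the end of all analgesia when it need not. Second, one assessor might follow the label and wait for pump-off while another follows the definition and does not, so that the same patient could be given two different times. Because discharge comes after recovery time, such a discrepancy could in principle carry through to length of stay.

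**Working it through.** **1. Which outcome carries the trial.** The opening paragraph gives the sample-size inputs: a difference of 1 day in length of stay, SD 2 days, α = 0.05 (two-sided assumed, since sidedness is not stated), power 90%, loss to follow-up 5%.

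- Standardised difference: 1 / 2 = 0.5.
- Two-sample t test: 85.03, rounded up to 86 per group.
- Allowing for loss: 86 / (1 − 0.05) = 90.5, rounded up to 91 per group; 2 × 91 = 182. This is the plan's figure.
- The normal approximation gives 85, and 85 / 0.95 = 89.5, so 90. A one-sided test gives 69, and 69 / 0.95 = 72.6, so 73, which does not match.

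The sample size therefore rests on length of stay alone, and no reading of the pain criterion alters it. The statistical analysis paragraph names no outcome and assigns recovery time no role.

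**2. The two texts side by side.** Step 8 says that a pump is connected and says nothing about recovery time. The recovery-time paragraph says what counts as meeting the pain criterion and says nothing about the pump. Both can be followed at once, so they do not contradict each other. The mismatch lies inside one clause, between a short label and the definition attached to it. A definition supplied with its label governs, and it gives the analyst a usable rule: score at or below 3, and no intravenous analgesic.

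**3. Size of the discrepancy.** For one patient, let R_w be recovery time as written, T_off the time the pump stops, and R_e the first time all four criteria hold with the pump off.

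- R_e ≥ max(R_w, T_off).
- Gap = R_e − R_w ≥ max(0, T_off − R_w).
- The between-arm difference in mean recovery time would change by (mean gap, intervention) − (mean gap, control), which is 0 if the two mean gaps are equal.

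The document gives neither T_off nor R_w. The lower bound on the gap is zero whenever the pump stops before the other criteria are met, and nothing in the document sets an upper bound. The figure of 182 counts patients to whom the definition applies; it does not count patients affected.

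**4. What a second version would add.** Suppose R_e were reported beside R_w, with discharge and analgesia left alone.

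- Length of stay would be unchanged in every patient, because discharge would still follow R_w.
- R_e would be equal to or later than R_w in both arms, and the delay would depend partly on when ward staff remove pumps.
- R_e would be unobserved in any patient who left before it was reached.
- R_e would still count a patient taking oral analgesics as meeting the criterion, so the label would remain inexact.

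**The case for a change.** The best case for acting is that recovery time is a measured quantity and a gate to discharge, so it should mean what it is called. The pump's probable removal before a patient goes home does not settle the matter, because recovery time comes earlier than discharge and no text says the pump is off by then. The document also describes no blinding of outcome assessors, so the two readings could be applied unevenly between arms. A clarifying sentence and one recorded time per patient would cost little.

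Part of this stands. The literal gap is real, nothing elsewhere closes it, and uneven application cannot be excluded from the text alone. But nothing in the document points to a difference between arms in pump use or in how the criterion is read. The analgesia steps are common to both arms, and the ward-management paragraph applies the same discharge criteria to all patients. Discharge also depends on the patient's own judgement, so the route from this wording to length of stay is indirect. A clarifying sentence would be harmless, but it would tidy a label and would not repair an analysis. The additional analysis is the only substantive proposal, and its weaknesses in step 4 of the working make it a matter of preference.

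**Conclusion.** No change to the plan is needed. This is a labelling imprecision with a workable definition beside it. A trial run and analysed as written would report recovery time under a stated rule common to both arms, and length of stay, the outcome behind the 91 per arm, would be analysed as planned. Analysts can handle the point by giving the operational definition wherever recovery time is reported.

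The size of the discrepancy cannot be computed from the document. The conclusion rests on three assumptions: assessors apply the definition as written, pump use does not differ by arm in a way that feeds into that definition, and recovery time keeps the unranked role it has now. The document contains nothing against the first two, though it does not prove them. Nothing here judges how long epidural analgesia should run or whether it should count against recovery.

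### Randomisation is stratified by sex, disease character and age, but length of stay gets only unadjusted tests: valid, with some precision given up if those factors predict stay

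*Combined protocol and SAP*

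**What the plan says.** The randomisation paragraph states: "A stratified randomization with three factors including sex, disease character and age will be performed by statistician to ensure an even spread". The sample size in the opening paragraph rests on "an absolute reduction in the length of the hospital stay by 1 day" with "standard deviation 2 days". Post-operative stay is also the one outcome named when the protocol says what will be evaluated: "The outcomes such as the length of hospital stay after surgery will be recorded and analyzed".

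The Statistical analysis paragraph describes continuous data by their shape ("Mean (SD) for normally distributed data or median (Q1, Q3) for skewed data will be calculated for continuous variables") and tests them with "t test or Mann-Whitney U test or Analysis of Variance for Repeated Measures". Stay is measured once per patient, so repeated-measures analysis does not apply. The choice for stay is a t test or a Mann-Whitney test. No covariate, stratified test or model appears anywhere in the document, for either the intention-to-treat or the per-protocol set.

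**The concern.** Stratifying on a factor implies that it may influence outcome. A plain two-group test ignores it, so any variation in stay due to sex, disease character or age remains in the error term. The estimate of days saved is then less precise than the same data allow. The information needed is already held for every randomised patient, because the list is stratified on it. At stake is the width of the interval on days saved and a little power, which matter mainly if the result is borderline.

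**Working it through.** **Inputs from the opening paragraph.** Difference 1 day, SD 2 days, alpha 0.05, power 90%, loss 5%, 91 per group.

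**Assumptions.** The test is two-sided (sidedness is not stated). R², the share of the variance of stay explained by the three factors, is not in the documents and is taken as 0, 0.10 or 0.20.

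**1. The plan's own figure.** n per group = 2 × (1.960 + 1.282)² × 2² / 1² = 84.06, so 85; 85/0.95 = 89.5, so 90. With the t distribution the requirement is 85.03, so 86; 86/0.95 = 90.5, so 91. The stated 91 reproduces. A one-sided test gives 69, or 73 after loss, and does not. The trial was therefore sized for the unadjusted comparison that it plans.

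**2. Closed form with perfect balance within strata.** Take 86 evaluable per group (91 × 0.95 = 86.45).
- Unadjusted SE = 2 × √(2/86) = 0.305; half-width = 1.96 × 0.305 = 0.598 day.
- Adjusted half-width = 0.598 × √(1 − R²) = 0.598 / 0.567 / 0.535 day for R² = 0 / 0.10 / 0.20.
- True type I error of the unadjusted test = 2 × [1 − Φ(1.96/√(1 − R²))] = 5.0 / 3.9 / 2.8%.

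**3. Simulation, normal errors.** 182 patients, 8 equal strata, 5% lost at random, 20,000 trials per setting. The t test is compared with a linear model on arm plus the three factors.

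| Lists | R² | Half-width, unadjusted / adjusted (days) | Power, unadjusted / adjusted | Type I error, t test |
|---|---|---|---|---|
| No blocks | 0 | 0.60 / 0.607 | 90.6 / 90.2% | 5.2% |
| No blocks | 0.10 | 0.60 / 0.576 | 90.7 / 92.5% | 5.0% |
| No blocks | 0.20 | 0.60 / 0.543 | 90.5 / 95.1% | 4.8% |
| Blocks of 4 | 0 | 0.60 / 0.600 | 90.9 / 90.9% | 4.8% |
| Blocks of 4 | 0.10 | 0.60 / 0.570 | 91.7 / 93.0% | 4.1% |
| Blocks of 4 | 0.20 | 0.60 / 0.537 | 92.9 / 95.6% | 3.0% |

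The blocked rows agree with the closed form to within about 0.2 point on type I error. The t test is conservative only when the lists are blocked.

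**4. Skewed stay.** Same design, with lognormal errors, an assumed mean of 4 or 6 whole days and a constant 1-day shift. The comparison is a linear model on the ranks of stay (arm plus the three factors) against the plain Mann-Whitney test. Power changes by -0.3 to 0 / +1.2 to +2.3 / +2.3 to +4.6 points at R² = 0 / 0.10 / 0.20. For example, with R² 0.10, mean 6 and no blocks, it is 91.8% for Mann-Whitney and 94.0% for adjusted ranks. Across steps 3 and 4, the type I error of the adjusted tests was 4.4-5.3%.

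**5. Linear model on days as the primary test under skew, R² = 0.** Against Mann-Whitney, a constant 1-day shift costs the linear model 3.9 to 7.8 points. With a proportional effect of the same mean size, power is 96.8% (Mann-Whitney) against 95.3% (linear) at mean 4, and 94.8% against 94.3% at mean 6: a loss of 1.5 and 0.5 points.

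**The case against.** The strongest reply is that this is a preference about efficiency. Sample size and analysis agree with each other, nothing is biased, and the planned power is kept. That stands, and it limits the weight of the point.

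The gain also rests on an R² that the documents do not give, and the population suggests a weak link. Entry is limited to "American Society of Anesthesiology physical status I and II and aged 18 to 65 years", diabetes and BMI of 30 or more are excluded, ward management is common to both arms, and the day of discharge depends partly on the patient's own judgement. This stands too, which is why the range starts at zero.

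Equal strata favour adjustment. With the same factor effects as at R² 0.10 (skewed stay, mean 6, no blocks) but splits of 50/50, 85/15 and 70/30, power was 92.7% for Mann-Whitney and 94.4% for adjusted ranks, a gain of 1.7 points. With equal splits it was 91.6% and 94.5%, a gain of 2.9. The benefit shrinks but remains.

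Three stronger readings are tempting:
- **A reader might infer that ignoring the strata invalidates the tests or inflates false positives.** It does not: type I error stays at about 5% or falls below it.
- **A reader might infer that the tests are conservative as planned.** That needs blocks within strata. The stated aim of an even spread suggests balance was intended, but no blocks are mentioned.
- **A reader might infer that a linear model under skew always costs 4-8 points.** That holds only for a constant 1-day shift. At mean 4 days and R² = 0, that model puts 1.6% of stays at zero or below, which is implausible after nephrectomy.

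**Conclusion.** The point holds as a minor matter of precision, worth considering. The factors used to randomise do not appear in the analysis of the outcome the trial was sized on.

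At an assumed R² of 0.10 the interval could be about 0.02-0.03 day narrower on each side, with about 2 points more power. At 0.20 the gain is about 0.06 day and 2.5 to 5 points. At zero nothing is gained. If the lists are blocked, the unadjusted test runs at about 4% (R² 0.10) or 3% (R² 0.20) instead of 5%.

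These sizes rest on the assumed R², near-equal strata, an SD of 2 days and random 5% loss. The omission itself is plain from the text; the size of the gain is not known.

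**What to change.** Include sex, disease character and age, at the levels used in the randomisation list, in the primary analysis of post-operative stay. Estimate the difference in mean days and its 95% confidence interval from a linear model on arm plus the three factors; this targets the same mean difference as the unadjusted comparison. If stay is skewed and a rank test is used, replace the plain Mann-Whitney test with a linear model on the ranks of stay, with arm plus the three factors. Keep the unadjusted test as a sensitivity analysis.

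The cost is analysis-plan wording, with no new data. If the factors do not predict stay, the linear model loses under 1 point of power and under 0.01 day of half-width against the t test. Adjusted ranks lose 0-0.3 point against Mann-Whitney with 8 strata, and 0.3-0.6 with 12 unblocked strata. If the linear model on days is also made the primary test for skewed stay, its power relative to Mann-Whitney depends on the form of the effect: roughly 4-8 points lower for a constant shift, about 0.5-1.5 lower for a proportional one. The adjusted rank test avoids that cost.
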